## **Overall goals and background**

Atopic Dermatitis (AD) is a common skin condition affecting 10-20% of children in the United States. Atopic dermatitis is associated with chronic pruritus and inflammation leading to significant discomfort, stress and social stigma. Wet wraps (corticosteroid contained in a vehicle wrapped in wet dressings) have been used for many years and are an effective means of improving moderate to severe atopic dermatitis. A wet wrap's efficacy is a product of a corticosteroid's activity at the site of action, as well as patient compliance. Wet wraps can be messy and difficult to use for patients and families and has been associated with variable adherence. Interestingly, little research has been done regarding wet wrap comparable efficacy and patient tolerability. Recent studies have shown that wet wraps with topical steroids are superior to emollients alone. However, there are no studies comparing different vehicles for topical steroids when used for this treatment.

The purpose of this study is to

1. Compare efficacy of 0.1% triamcinolone containing wet wrap as an ointment or as a cream formulation in patients with moderate to severe atopic dermatitis

2. The relative patient/subject acceptance and adherence will also be compared between the two wet wrap types

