# Hypothesis

Significant controversy exists on the optimal vehicle for wet wraps. Some advocate for cream (oil in water) formulations because they are hydrophilic and therefore may be absorbed better in the aqueous environment of a wet dressing. Others prefer ointments (water in oil) because they are more potent than creams. We hypothesize that the overall difference will be negligible and that patient preference should be the largest factor in deciding which to use. Many patients prefer creams because they are lighter and more elegant while others prefer the thickness of ointments.

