## **Methodology and Rationale**

### Inclusion Criteria

- 1. Patients between the ages of 3-17 experiencing a symmetric, bilateral flare of atopic dermatitis
- 2. The flares must reach a certain threshold for inclusion based on the investigator's global assessment scale

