#### **Methods**

Patients and/or parents will be asked to sign an informed consent authorizing their participation in the study. All information will be de-identified to protect the patient's privacy.

In this study, we will examine the effectiveness of wet wraps with topical steroids in different formulations for patients with a history of atopic dermatitis who are experiencing an acute flare. A validated clinical tool such Investigator's Global Assessment (IGA) will be used in order to assess severity of the condition as well as demonstrate the appropriateness of using wet wrap therapy as a treatment modality. IGA will measure intensity of the atopic dermatitis regarding erythema, lichenification, swelling and excoriation as well as subjective symptoms of the patient on a numeric scale. The treating clinician will be asked to rate their assessment before and after therapy.

Patients will be asked to apply a topical steroid in a cream formulation to one extremity and then apply the same topical steroid in an ointment formulation to the other using the wet wrap technique. One of the investigators or nursing staff will provide detailed instructions to the patient and parents on how to perform the wet dressing (this is already routinely done for patients initiating wet wrap therapy in the pediatric dermatology clinic). Patients will also be given a sealed and coded envelope containing

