instructions to apply one steroid formulation to the right extremity and the other to the left. In this manner the providers will be blinded to treatment modality during the follow-up visit. Only the research coordinator will have access to the envelope code key. An additional handout will also be provided to reinforce appropriate treatment technique. After several days (3-5) the patient will return to the dermatology clinic for a nurse visit and evaluation of any improvement of the affected areas as well as comparison of improvement of the right and left extremities. The physician investigator will examine the patient and measure improvement using the IGA. Detailed photos of the affected areas will also be taken. After a certain number of patients have enrolled in the study and completed it, the de-identified data will be examined by a statistician for comparison. Other studies evaluating the effectiveness of wet wraps have commonly had 40-50 patients enrolled which will likely be the target of this study. The statistician will compare the IGA before and after treatment on each side to allow for interpretation of the data. Stratification of data may include ages and/or severity (moderate vs severe).

Patient Oriented Eczema Measure (POEM) and/or a Quality of Life (QoL) index will also be provided before and after treatment in order to determine the patient's point of view regarding their management using validated tools. They will also be asked their opinion regarding if one side was better controlled than the other, if at all, as well as their personal preference for treatment of choice.

Compliance will be determined by weighing the medication before and after each visit and a medication calendar.

The participating clinicians, including myself, will be performing the IGA before and after treatment. I will also be responsible for data collection as well as help with statistical analysis under the mentorship of [name] and possibly a statistician if needed.

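### Aim 1 compares cream with ointment, but the only analysis contrast spelled out is IGA before versus after on each side; no between-side estimate, confidence interval or test is defined

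*Combined protocol and SAP*

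**What the plan says.** The first aim, under Overall goals and background, is to "Compare efficacy of 0.1% triamcinolone containing wet wrap as an ointment or as a cream formulation in patients with moderate to severe atopic dermatitis". The Methods section gives each patient both vehicles, cream on one extremity and then to "apply the same topical steroid in an ointment formulation to the other using the wet wrap technique". A sealed, coded envelope holds "instructions to apply one steroid formulation to the right extremity and the other to the left", and the research coordinator keeps the code key.

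Three statements in Methods bear on the comparison:

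- The follow-up visit includes a "comparison of improvement of the right and left extremities".
- De-identified data then go to a statistician for comparison; what is compared with what is not said.
- The one contrast spelled out for the analysis is: "The statistician will compare the IGA before and after treatment on each side to allow for interpretation of the data".

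The Hypothesis section states: "We hypothesize that the overall difference will be negligible and that patient preference should be the largest factor in deciding which to use". No section says what result would support that.

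**The concern.** A before/after test on one side asks whether that side improved. Aim 1 asks whether the two sides improved by different amounts. These are different questions, and here the first is largely uninformative about the second. Both limbs get the same steroid under wraps that the background section says "are an effective means of improving moderate to severe atopic dermatitis", so both sides may improve under either answer to aim 1.

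If the sentence is followed literally, two misreadings are open:

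- Improvement on both sides fits equal vehicles and also a real difference between them.
- One side significant and the other not can occur when the vehicles are equal.

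The stated hypothesis makes the first more serious. Because the investigators expect a negligible difference, improvement on both sides, or a non-significant comparison, could be taken as confirmation when neither is evidence of no difference.

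**Working it through.** **The plan's own figure.** The only number that bears on precision is the target of 40-50 patients, chosen by analogy with other wet-wrap studies. It cannot be reproduced: the documents give no alpha, power, effect size, SD, margin or dropout rate. What follows is therefore illustration.

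**Assumptions (not in the documents).** IGA change per side is approximately normal with SD σ of 0.5 to 1 point. The correlation ρ between a patient's two sides is 0.3 to 0.7. All patients are evaluable, and tests are two-sided 5% t-tests.

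**Step 1: separate before/after tests against one paired test.** Simulated trials with n = 45, σ = 1; ranges are over ρ = 0.3 to 0.7.

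| True mean improvement, two sides | Both sides significant | One significant, one not | Paired between-side test rejects |
|---|---|---|---|
| 1.0 / 1.0 | about 100% | about 0% | 5% |
| 1.5 / 1.0 | about 100% | about 0% | 79-99% |
| 1.0 / 0.5 | about 91% | about 9% | 79-99% |
| 0.3 / 0.3 | 30-38% | 26-41% | 5% |
| 0.5 / 0.5 | 83-86% | 10-15% | 5% |

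The first two rows carry the point: the before/after tests give the same answer with and without a half-point difference between vehicles. In the third row one side improves twice as much as the other, and both are still significant in about 91% of trials (87-93% for n = 40-50).

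**Step 2: sensitivity.**

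- Rounding changes to whole points (σ = 1): both sides significant in about 100% at 1.0/1.0 and at 1.5/1.0, with paired rejection 5% and 75-96%.
- σ = 0.5: again about 100% both significant in each case, with paired rejection 5% and about 100%.
- The discordance result is less stable. At σ = 0.5, an equal improvement of 0.3 point gives one-significant-one-not in only about 3-5% of trials, and 0.5 point in about 0%. It returns to 10-40% only if the improvement shrinks to 0.15-0.25 point.

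**Step 3: what a paired analysis would deliver.** The SD of the within-patient difference is σ√(2(1−ρ)), and the 95% CI half-width is t(0.975, n−1) × that SD / √n.

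- Smallest: σ = 0.5, ρ = 0.7, n = 50. SD = 0.5 × √0.6 = 0.387; half-width = 2.010 × 0.387 / √50 = 0.11 point.
- Largest: σ = 1, ρ = 0.3, n = 40. SD = √1.4 = 1.183; half-width = 2.023 × 1.183 / √40 = 0.38 point.

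In the same two cells, a true 0.3-point difference is non-significant (noncentral t) in 0.03% and 65% of trials. A non-significant paired test therefore cannot, by itself, support a negligible difference.

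**Step 4: can the trial show a negligible difference?** If the vehicles are truly equal, the chance that the whole 95% CI lies inside a margin, for n = 40-50 and ρ = 0.3-0.7, is:

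| Illustrative margin | σ = 1 | σ = 0.5 |
|---|---|---|
| ±0.3 point | 0.2-53% | 76-99.9% |
| ±0.5 point | 48-99% | about 100% |

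These margins are illustrations, not proposals.

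**The case against.** The strongest reply is that the sentence describes inputs, not tests. With an ointment-versus-cream aim, a right-left comparison at the visit, a code key and a statistician examining the data, comparing IGA before and after on each side may simply mean computing each side's change so that the changes can be compared. The text names no test of any kind. That reading is fair, and it means the fault is an undefined contrast rather than a wrong analysis deliberately chosen. It does not supply the definition. The right-left wording belongs to a visit at which providers are blinded to formulation, and no estimate or test is attached to it.

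Three further points partly stand:

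- **Discordant results need weak improvement relative to the SD.** If wet wraps work as well as the background section says, this harm is an edge case. It should be treated as secondary to the both-sides-improved problem, which does not depend on weak effects.
- **Statistical support may be available.** The Budget section seeks money for statistical analysis, and Methods twice has a statistician examining or comparing data. But Methods closes by making a statistician's help conditional on need, so the written text may be the main guide.
- **The Relevance to Professional Career section asks whether one formulation is superior.** That question needs only the paired estimate and CI. A margin is needed only for the no-difference claim, which the Hypothesis section does make. The paired estimate serves both.

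**Conclusion.** The concern holds. Aim 1 has no defined analysis, and the one contrast spelled out cannot answer it if taken literally. That conclusion comes from the text and does not depend on the illustrative figures: a within-side test is not a test of the difference between sides. The size does rest on assumed SDs, correlations and normality, because the documents define neither the IGA scale nor its variability. Within those assumptions, a half-point vehicle difference on top of a 1-point improvement is invisible to separate before/after tests in essentially every trial.

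This should be fixed, but it is not fatal. The aim 1 data are not lost, and the contrast can still be set in writing before unblinding.

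**What to change.** Replace the sentence in Methods with a paragraph along these lines:

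> Primary analysis: after decoding sides with the code key, the within-patient difference (ointment side minus cream side) in IGA change from baseline will be estimated with a 95% CI and tested with a paired t-test, with the Wilcoxon signed-rank test as a sensitivity analysis. Within-side before/after changes are descriptive. Neither a non-significant result nor improvement on both sides will be taken as showing a negligible difference; that claim will rest on the CI, read against a margin stated before unblinding.

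A paired ordinal method is a reasonable alternative, and may suit the scale better once it is defined, provided one method is named in advance.

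Two adjustments should be conditional:

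- **Baseline side difference:** adjust only if it varies. Entry requires patients to be "experiencing a symmetric, bilateral flare of atopic dermatitis", so it may be zero for nearly everyone. If 2% of patients differed (an assumed rate), the chance that none of 45 did would be 0.98^45 = 0.40.
- **Which side received ointment:** adjust only if this varies between patients, which Methods does not say.

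The cost is one paragraph and agreement on a margin. IGA before and after on each side and the code key are already planned, so no new data are needed. The investigators should set the margin knowing that the expected CI half-width is about 0.11-0.38 point under the assumptions above; a margin near or below the half-width could rarely be met with 40-50 patients.

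### The IGA comparison, most naturally read as one of change scores, has no stated adjustment for each limb's baseline grade; adding one would gain precision at almost no cost

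*Combined protocol and SAP*

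**What the plan says.** All the relevant text is in the Methods and Inclusion Criteria sections of the combined protocol and SAP.

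- **Design.** Each child receives "instructions to apply one steroid formulation to the right extremity and the other to the left", so cream and ointment are compared within the child.
- **Ratings.** "The treating clinician will be asked to rate their assessment before and after therapy". At the return visit, "The physician investigator will examine the patient and measure improvement using the IGA".
- **Between-side comparison.** The visit includes "evaluation of any improvement of the affected areas as well as comparison of improvement of the right and left extremities".
- **Analysis.** "The statistician will compare the IGA before and after treatment on each side to allow for interpretation of the data". This is the only sentence on how IGA will be analysed. It names no statistic, test, model or covariate.
- **Use of baseline.** Stratifying by age or by moderate versus severe disease is offered as an option. Nothing uses the baseline grade of each limb.
- **Eligibility.** "Patients between the ages of 3-17 experiencing a symmetric, bilateral flare of atopic dermatitis".
- **Size.** "Other studies evaluating the effectiveness of wet wraps have commonly had 40-50 patients enrolled which will likely be the target of this study".

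**The concern.** If improvement is taken as follow-up minus baseline on each limb, the cream-minus-ointment contrast combines four separately scored grades. It then carries the scoring error of both baseline grades as well as that of both follow-up grades. In children enrolled because the flare is symmetric, much of any observed right-left difference at baseline is likely to be rating or rounding noise. A change score passes that noise in full into the treatment comparison, whereas regression on the baseline difference removes the part that does not predict follow-up.

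Optional stratification by moderate versus severe disease would not do this job. It classifies children and says nothing about the difference between a child's two limbs.

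Precision matters here because the Hypothesis section expects a negligible difference, and the section on professional relevance would let patient preference decide if there is none. That conclusion needs a narrow interval for cream minus ointment, and the sample size was not chosen to deliver one.

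**Working it through.** **The plan's own figure.** The target of 40-50 cannot be reproduced, because no alpha, power, effect or SD is given. For context, assuming a two-sided 5% test, 80% power and a normal approximation, the detectable paired effect is (1.960 + 0.842)/√n. That is 2.802/√40 = 0.44 and 2.802/√50 = 0.40 SDs of whichever paired difference is analysed. A contrast with a smaller SD therefore detects a smaller effect in IGA grades.

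**Algebra.** Let d0 and d1 be a child's cream-minus-ointment IGA difference at baseline and follow-up, with variances v0 and v1, covariance c, correlation r and slope b = c/v0. Per child:

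- change contrast: v0 + v1 − 2c
- baseline-adjusted contrast: v1 − c²/v0
- excess of change over adjusted: v0 − 2c + c²/v0 = v0(1 − b)², which is never negative

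The excess vanishes if b = 1 or v0 = 0. It is largest when baseline differences are frequent but do not predict follow-up.

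**Closed-form illustration (r and v0/v1 assumed).** With v0 = v1, adjusted/change = (1 + r)/2:

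| r | 0 | 0.3 | 0.5 | 0.7 | 0.9 |
|---|---|---|---|---|---|
| adjusted/change variance | 0.50 | 0.65 | 0.75 | 0.85 | 0.95 |

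With v0/v1 = 0.25, adjusted/change = (1 − r²)/(1.25 − r):

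| r | 0 | 0.3 | 0.5 | 0.7 |
|---|---|---|---|---|
| adjusted/change variance | 0.80 | 0.96 | 1.00 | 0.93 |

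**Simulation (all inputs assumed; 4,000 trials per setting; integer grades 0-4; independent rating errors).**

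1. *Limbs truly equal at baseline.* Limb-level SD 0.2-0.4, rating SD 0.15-0.35, vehicle effect 0.25 grade, N = 40 or 50. Baseline grades still differed in 17-38% of children. Adjusted/change variance was 0.56-0.79; a repeat at N = 45 gave 0.55-0.79. Both estimators had the same mean.
2. *Real baseline asymmetry.* At N = 45 the ratio was 0.59-0.84. Another run, with asymmetry SD 0.2-0.4, gave 0.64-0.92, so the upper end is soft.
3. *A differently built model, N = 45, rating SD 0.3-0.5.* With limbs equal and rating SD 0.3, the variances were 0.02161 (change) and 0.01483 (adjusted), a ratio of 0.69. The 95% half-widths are 1.96 × √0.02161 = 0.29 grade and 1.96 × √0.01483 = 0.24 grade. With asymmetry SD 0.4 the variances were 0.02115 and 0.01809, a ratio of 0.86.
4. *Screening on symmetry.* If 75% of children with unequal baseline grades are excluded (assumed), the ratio is about 0.80-0.97. If all are excluded, v0 = 0 and it is 1.00.

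**Converted to standard errors (1/√ratio).** At 0.55 the change-score SE is 35% larger, and at 0.85 it is 8% larger. At 0.80 it is 12% larger, and at 0.97 it is 2% larger.

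**Cost of estimating the slope.** This is roughly 1/(N − 3) of variance: 1/37 = 2.7% at N = 40 and 1/47 = 2.1% at N = 50.

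**The case against.** **The plan does not commit to change scores.** The analysis sentence fits separate before-after tests on each side just as well, and it does not rule out adjustment. A reader might infer that raw change has been prescribed, but the documents never define the statistic. This stands. The more basic gap is that no between-limb contrast is defined, and the fix must supply one under either reading.

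**The symmetry criterion may remove most of the gain.** Children with visibly unequal limbs may not be enrolled. With equal baseline grades the two analyses are identical, and with heavy screening the gain is a few per cent of the SE. This also stands. The documents do not say how symmetry is judged, so neither end of the range can be excluded.

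**Rating errors may be shared.** Both limbs of a child would presumably be rated at the same visit. If half the rating variance is common to the two limbs, the simulated ratios (limbs truly equal, no screening) become 0.60-0.85. If 90% is common, they become 0.72-0.94. The gain shrinks, but its direction does not change.

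**The scale is assumed.** The plan mentions only a numeric scale, without a range, so rounding to integers 0-4 is an assumption that contributes to the simulated noise.

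**Linear regression on coarse grades is one choice among several.** A mixed or ordinal model would be equally defensible. What matters is that limb baseline enters the model.

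**Conclusion.** The point holds as a cheap improvement in precision. No adjustment for limb baseline IGA is stated. On the natural reading the contrast is one of change scores, and in large samples that is never more precise than the adjusted contrast. The illustrated adjusted/change variance ratio is about 0.55-0.85 without screening on limb symmetry, about 0.8-0.97 with heavy screening, and 1.00 if baseline grades never differ. These figures rest on an assumed 0-4 scale, assumed SDs and independent rating errors. None of those inputs is in the documents, so no single figure for the gain can be claimed.

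Two stronger inferences are not supported.

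- *That change scores double the noise.* This is true only of rating-error variance relative to a follow-up-only score, with equal and independent errors. Against the adjusted analysis, with v0 = v1, total variance doubles only at r = 0.
- *That the unadjusted result would be biased or the trial invalid.* With random allocation of formulation to side, both contrasts estimate the same effect. The documents describe sealed, coded envelopes but do not state that the allocation is random, so this rests on that assumption.

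**What to change.** Replace the analysis sentence with one paired between-limb analysis, for example:

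*For each child, the follow-up IGA difference (cream limb minus ointment limb) will be regressed on the baseline IGA difference (cream limb minus ointment limb). The intercept, with its 95% confidence interval, is the estimated vehicle effect. If no child has a baseline difference, the mean follow-up difference will be reported.*

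An equivalent mixed model with a child effect and limb baseline, or an ordinal version, is acceptable. Raw changes per limb may be shown as supportive results. The plan should also say that each limb receives its own IGA grade at baseline, which the present wording implies but does not state.

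The cost is one sentence, one degree of freedom (about 2-3% of variance at 40-50 children) and reliance on a linear model for coarse grades if that version is used. No new data or visits are needed.

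### The side-to-side IGA comparison makes no planned use of the compliance data and has no record of which product went on which limb, so swaps and shared misses would push the result toward the hypothesized negligible difference

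*Combined protocol and SAP*

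**What the plan says.** The Hypothesis section sets the expected result: "We hypothesize that the overall difference will be negligible and that patient preference should be the largest factor in deciding which to use". Relevance to Professional Career repeats the consequence: if no clinical difference is found, preference is to guide the choice.

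Overall goals and background names compliance as one of the two determinants of wet-wrap efficacy and adds that "Wet wraps can be messy and difficult to use for patients and families and has been associated with variable adherence". Its second purpose is to compare acceptance and adherence between the two wrap types.

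Under Methods, each family receives a sealed, coded envelope with "instructions to apply one steroid formulation to the right extremity and the other to the left". Only the research coordinator holds the code key. Staff teach how to do the wet dressing, and a handout reinforces technique. On compliance, "Compliance will be determined by weighing the medication before and after each visit and a medication calendar". The efficacy analysis is one sentence: "The statistician will compare the IGA before and after treatment on each side to allow for interpretation of the data". Possible stratification is by age or severity. No analysis set, adherence threshold, sensitivity analysis or margin for a negligible difference is given.

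**The concern.** The plan says that compliance drives efficacy, expects it to vary and measures it, but does not bring it into the efficacy comparison. In a trial meant to show a difference, dilution works against the investigators' hypothesis. Here, swaps and misses shared by both limbs work in its favour. A small observed difference could mean that the vehicles perform alike, or that the assigned contrast was only partly delivered, and the planned data could not fully separate the two.

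The within-child design makes swaps costly, because a swap reverses the child's contrast instead of merely removing it. Tube weights cannot show a swap: each product can be used in the expected amount on the wrong limb. No limb-level calendar entry is described. A swap that is not recorded at the time cannot be recovered later.

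**Working it through.** **Inputs from the documents.** Target of 40-50 children, taken from the size of other wet-wrap studies and not from a calculation; return visit after 3-5 days; adherence described as variable, with no rate. No alpha, power, effect size, standard deviation or margin is stated, so there is no power figure to reproduce. Everything numerical below rests on assumed values and shows direction and scale only.

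**1. Swaps and shared misses.** Let a share q of children treat neither limb, and let a share s of the remaining applications be swapped. If response is proportional to use, the expected difference is the true one times (1 - q)(1 - 2s). For an assumed true difference of 0.5 IGA step:

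- q = 10%, s = 0: 0.90 × 1.00 = 0.90, seen as 0.45
- q = 20%, s = 5%: 0.80 × 0.90 = 0.72, seen as 0.36
- q = 30%, s = 10%: 0.70 × 0.80 = 0.56, seen as 0.28

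**2. Effect on power.** Assume a two-sided alpha of 0.05, 80% power with perfect adherence, a paired normal approximation, and a standard deviation of the within-child difference that adherence does not change. The detectable standardized difference is (1.960 + 0.842)/√n, which is 0.44 at n = 40 and 0.40 at n = 50. With the contrast multiplied by k, power is Φ(2.802k - 1.960) at either n. Here k = 1 - 2f if a share f of children swap limbs, and k = 1 - f if both limbs miss a share f.

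| f | Power, swaps | Power, shared misses |
|---|---|---|
| 5% | 71% | 76% |
| 10% | 61% | 71% |
| 20% | 39% | 61% |

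**3. Effect on a no-difference claim.** Suppose that negligible were tested by two one-sided 5% tests with an assumed margin of 0.5 SD, and that the true difference lay exactly at the margin. The chance of wrongly concluding equivalence is nominally 5%. At f = 5%, 10% and 20% it becomes:

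- n = 40: 9%, 16% and 35% with swaps; 7%, 9% and 16% with shared misses
- n = 50: 10%, 17% and 41% with swaps; 7%, 10% and 17% with shared misses

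**4. Misses that differ by vehicle.** With true improvements E_o (ointment) and E_c (cream) and missed shares m_o and m_c, the observed ointment-minus-cream difference is (1 - m_o)E_o - (1 - m_c)E_c. Assumed values, in IGA points:

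- E_o = E_c = 1.5, 20% missed on ointment only: 0.8 × 1.5 - 1.5 = -0.30, a difference where none exists
- E_o = 1.5, E_c = 1.2 (true +0.30), 20% missed on ointment only: 1.20 - 1.20 = 0.00, hidden
- Same, 20% missed on cream only: 1.50 - 0.96 = +0.54, widened
- Same, 30% missed on ointment and 10% on cream: 1.05 - 1.08 = -0.03, reversed

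So the direction is fixed only for swaps and for misses shared by both limbs.

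**The case against.** **The direction of bias is not general.** A reader might infer that poor adherence of any kind makes the vehicles look alike. The documents do not support that. The second purpose treats a difference in adherence between wrap types as possible, and the Hypothesis section says that some patients prefer creams and others ointments. Misses specific to one vehicle are therefore foreseeable, and step 4 shows that they can go either way. This objection stands and limits the claim about direction. It does not remove the reason to look at adherence beside efficacy.

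**An as-assigned comparison is legitimate.** Methods speaks of effectiveness, and the background counts compliance as part of efficacy. A comparison that includes real-life adherence answers that question. This also stands: the as-assigned analysis should remain the main one, and the lack of a second analysis is a gap rather than an outright error.

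**Much is silence rather than statement.** A reader might infer that every returning child enters the analysis, or that the compliance data go unused. Methods mentions children who enrolled and completed, without defining either an analysis set or completion, and adherence does serve the second purpose. The envelope does carry the side instruction; the envelope and handout texts are not in the documents, and nothing says whether tubes are labelled. This is a grant proposal written before IRB approval, so such details could still be added.

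**Labels could threaten the blind.** The author both rates IGA and is responsible for data collection, and no one is named to weigh the tubes. A tube of cream marked with a side would unblind a rater who saw it. This is correct, and any labelling has to deal with it.

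**Conclusion.** The point holds in limited form. The efficacy comparison makes no planned use of the compliance data, and no record is planned of which product went on which limb. Swaps and misses shared by both limbs dilute the contrast in favour of the study's own hypothesis; vehicle-specific misses distort it in a direction that cannot be predicted.

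The size is unknown. The figures above depend on assumed swap and miss rates, response proportional to use, and an assumed margin and power. They do not show that this trial will lose that much; with 3-5 days of treatment and two products that feel different, swaps may be rare. The documents neither support nor exclude the rates used.

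This is a worthwhile, low-cost improvement rather than a fatal flaw. It is best made before enrolment, because unrecorded swaps are lost and an adherent set chosen after the results are seen would carry little weight.

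**What to change.** 1. **Record what was applied where, without exposing raters.** The research coordinator marks each tube RIGHT or LEFT according to the envelope before dispensing. At return, the coordinator collects and weighs the tubes out of sight of anyone rating IGA, asks the family which tube went on which limb, and keeps all of this from raters until the IGA is recorded. The calendar gets a separate entry for each limb.
2. **Prespecify two analyses.** Keep the within-child, as-assigned IGA comparison as the main analysis. Add a sensitivity analysis in children with no reported swap and both limbs treated, using an adherence threshold fixed before unblinding from the calendar and tube weights. State that weights inform misses, not swaps.
3. **State how they will be read.** Report both estimates with confidence intervals. Do not describe the difference as negligible if the two disagree materially, or on the strength of non-significance in the smaller set alone.

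**Cost.** Two labels and a short question per child, a limb-level calendar, slightly more coordinator work, and one extra analysis. The second set will be smaller and not randomly selected, so it can only support or question the main result. Labelled tubes must be kept from raters throughout. A margin for a negligible difference is also missing; these steps do not supply one.
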